Grade 2 (> 1.5 and ≤ 3.0 × ULN)	Omit study treatment. Monitor LFTs c weekly, or more frequently if clinically indicated until resolved to ≤ grade 1, then resume nazartinib and capmatinib at the same dose level.
Grade 3 (> 3.0 and ≤ 10.0 × ULN) g	
Omit study treatment. Monitor LFTsc weekly, or more frequently if clinically indicated until resolved to ≤ grade 1, then resume nazartinib at the same dose level.
 
 
• If no recurrence of grade 3 toxicity after 7 days of nazartinib monotherapy, resume capmatinib at ↓ 1 dose level
 
• If recurrence of grade 3 toxicity on maintained dose level of nazartinib and ↓ 1 dose level of capmatinib, omit study treatment until resolved to ≤ grade 1, then resume nazartinib at same dose level and Capmatinib ↓ 1 dose level
 
• If recurrence of grade 3 toxicity during nazartinib monotherapy, omit study treatment until resolved to ≤ grade 1, then resume nazartinib at ↓ 1 dose level
 
• If no recurrence of grade 3 toxicity after 7 days of nazartinib monotherapy at ↓ 1 dose level, resume capmatinib at ↓ 1 dose level
 

Grade 4 (> 10.0 × ULN) g	
Discontinue participant permanently from capmatinib and nazartinib.
 
The participant should be monitored weekly (including LFTsc), or more frequently if clinically indicated, until total bilirubin has resolved to baseline or stabilization over 4 weeks.

Isolated AST or ALT elevation	
Grade 2 (> 3.0 and ≤ 5.0 × ULN)	
Maintain dose level of both drugs with LFTsc monitored per protocol.
 
Repeat LFTsc as soon as possible, preferably within 48-72 hours from awareness of the abnormal results; if abnormal lab values are confirmed upon the repeat test, then monitor LFTsc weekly, or more frequently if clinically indicated, until resolved to ≤ grade 1.

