Grade 3 (> 3.0 - 10.0 x ULN)	Omit dose until resolved to ≤ grade 1, then 
 
• If fully resolved in ≤ 7 days, resume at ↓ 1 dose level
 
• If fully resolved in > 7 days, permanently discontinue capmatinib treatment
 

Grade 4 (> 10.0 x ULN)	Mandatory: Permanently discontinue capmatinib treatment
Isolated AST or ALT elevation	
Grade 1 (> ULN - 3 x ULN)	Maintain dose level
Grade 2 (> 3.0 - 5.0 x ULN)	Maintain dose level
Grade 3 (> 5.0 - 20.0 x ULN)	Omit dose until resolved to ≤ grade 1 (or ≤ grade 2 if grade 2 elevation at baseline) then 
 
• If fully resolved in ≤ 7 days, then resume at the same dose level
 
• If fully resolved in > 7 days, resume at ↓ 1 dose level
 

Grade 4 (> 20.0 x ULN)	Mandatory: Permanently discontinue capmatinib treatment
Combined elevations of AST or ALT and Total Bilirubinb,c,d	
For participants with normal baseline ALT and AST and total bilirubin value: AST or ALT > 3.0 x ULN combined with total bilirubin > 2.0 x ULN without evidence of cholestasis or hemolysis OR For participants with elevated baseline AST or ALT or total bilirubin value:	Mandatory: Permanently discontinue capmatinib treatment

Worst toxicity CTCAE Gradea during a cycle of therapy	Recommendation
[AST or ALT > 3 x baseline] OR [AST or ALT > 8.0 x ULN], whichever is lower, combined with [total bilirubin > 2 x baseline AND > 2.0 x ULN] without evidence of cholestasis or hemolysis	
METABOLIC	
Amylase and/or lipase elevation	
Grade 1 (> ULN - 1.5 x ULN)	Maintain dose level
Grade 2 (> 1.5 - 2.0 x ULN; > 2.0 - 5.0 x ULN and asymptomatic)	Maintain dose level
Grade 3 (> 2.0 - 5.0 x ULN with signs or symptoms; > 5.0 x ULN and asymptomatic)	Omit the dose until resolved to ≤ grade 1, then 
 
• If fully resolved in ≤ 14 days, resume at the same dose level
 
• If fully resolved in > 14 days, then resume at ↓ 1 dose level
 

Grade 4 (> 5.0 x ULN with signs or symptoms)	Permanently discontinue capmatinib treatment
CARDIAC	
Electrocardiogram QT corrected (QTc) interval prolonged	
Grade 1 (QTcF 450-480 ms) Grade 2 (QTcF 481-500 ms)	Maintain dose level

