Worst toxicity CTCAE a Grade (value) during a cycle of therapy	Recommendations
HEMATOLOGICAL	
Neutrophil count decreased (ANC) Neutropenia	
Grade 1 (ANC <LLN - 1500/mm  )	Maintain dose level
Grade 2 (ANC <1500 - 1000/mm  )	Maintain dose level
Grade 3 (ANC <1000 - 500/mm  )	Omit dose until resolved ≤ Grade 2, then maintain dose level
Grade 4 (ANC <500/mm  )	Recommendation: omit dose until resolved to ≤ Grade 2, then resume at ↓ 1 dose level
Febrile Neutropenia	
(ANC <1.0 x 10  /L, fever ≥ 38.5°C)	Recommendation: omit dose until resolved, then resume at ↓ 1 dose level
Thrombocytopenia	
Grade 1 (PLT <LLN - 75,000/mm  )	May maintain dose level
Grade 2 (PLT <75,000 - 50,000/mm  )	May maintain dose level
Grade 3 (PLT <50,000 - 25,000/mm  )	
 
Recommendation: omit dose until resolved to ≤ Grade 1, then:
 
If fully resolved in ≤ 7 days, then resume at same dose level
 
If fully resolved in >7 days, then resume at ↓ 1 dose level
 

Grade 4 (PLT <25,000/mm  )	Recommendation: omit dose until resolved to ≤ Grade 1, then resume at ↓ 1 dose level
RENAL	
Serum creatinine	
Grade 1 (>ULN - 1.5 x ULN)-	May maintain dose level
Grade 2 (>1.5 – 3.0 x ULN)	Recommendation: omit dose until resolved to ≤ Grade 1 or baseline, then resume at same dose level
Grade 3 (>3.0 – 6.0 x ULN)	Recommendation: omit dose and discontinue nazartinib
Grade 4 (>6.0 x ULN)	Recommendation: omit dose and discontinue nazartinib
HEPATICb	
Isolated Total Bilirubin (for participant s with Gilbert Syndrome these dose modifications apply to changes in direct [conjugated] bilirubin only)	
Grade 1 (>ULN - 1.5 x ULN)	Recommendation: maintain dose level
Grade 2 (>1.5 - 3.0 x ULN)	Recommendation: omit dose. Monitor LFTs c weekly, or more frequently if clinically indicated until resolved to ≤ 1.5 x ULN, then: 
 
If fully resolved in ≤14 days, then resume at same dose level
 
If fully resolved in >14 days, then resume at ↓ 1 dose level
 

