Grade 3 (>3.0 - 10.0 x ULN  )	Recommendation: omit dose. Monitor LFTs c weekly, or more frequently if clinically indicated until resolved to ≤ 1.5 x ULN, then: 
 
If fully resolved in ≤14 days, then resume at ↓ 1 dose level
 

Worst toxicity CTCAE a Grade (value) during a cycle of therapy	Recommendations
	
 
If fully resolved in <math>\leq 14</math> days, then discontinue nazartinib. The participant should be monitored weekly (including LFTsb), or more frequently if clinically indicated, until total bilirubin has resolved to baseline or stabilization over 4 weeks.
 

Grade 4 (>10.0 x ULN g )	
Mandatory: Permanently discontinue nazartinib
 
The participant should be monitored weekly (including LFTsb), or more frequently if clinically indicated, until total bilirubin has resolved to baseline or stabilized over 4 weeks.

Isolated AST or ALT	
Grade 1: >ULN - 3.0 x ULN	Recommendation: maintain dose level
Grade 2: >3.0 - 5.0 x ULN AND For participants with baseline value $\leq 3.0$ x ULN	Recommendation: maintain dose level. Repeat LFTs b as soon as possible, preferably within 48- 72 hours from awareness of the abnormal results; if abnormal lab values are confirmed upon the repeat test, then monitor LFTs b weekly, or more frequently if clinically indicated, until resolved to $\leq 3.0$ x ULN
Grade 2: >3.0 - 5.0 x ULN AND For participants with baseline value > 3.0 -5.0 x ULN	Maintain dose level
Grade 3: >5.0 - 10.0 x ULN AND For participants with baseline value $\leq 3.0$ x ULN	
Recommendation: omit dose. Repeat LFTsb as soon as possible, preferably within 48-72 hours from awareness of the abnormal results; monitor LFTsb weekly, or more frequently if clinically indicated, until resolved to <math>\leq 3.0</math> x ULN
 
Then
 
 
If fully resolved in <math>\leq 14</math> days, resume at same dose level
 
If resolved in > 14 days, resume at <math>\downarrow</math> 1 dose level
 

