
e "Cholestasis" defined as: ALP elevation (>2xULN and R value< 2) in participants without bone metastasis, or elevation of ALP liver fraction in participants with bone metastasis
 
Note: The R value is calculated by dividing the ALT by the ALP, using multiples of the ULN for both values. It denotes the relative pattern of ALT and/or ALP elevation is due to cholestatic or hepatocellular liver injury
 
f If combined elevations of AST or ALT and total bilirubin do not meet the defined thresholds, please follow the instructions for isolated elevation of total bilirubin and isolated elevation of AST/ALT, and take a conservative action based on the degree of the elevations (e.g., discontinue treatment at the situation when omit dose is needed for one parameter and discontinue treatment is required for another parameter). After all elevations resolve to the defined thresholds that allow treatment re-initiation, re-start the treatment either at the same dose or at one dose lower if meeting a criterion for dose reduction
 
g Note: If total bilirubin > 3.0 x ULN is due to the indirect (non-conjugated) component only, and hemolysis as the etiology has been ruled out as per institutional guidelines (e.g., review of peripheral blood smear and haptoglobin determination), then ↓ 1 dose level and continue treatment at the discretion of the investigator.
 
h A CT scan or other imaging study to assess the pancreas, liver, and gallbladder must be performed within 1 week of the first occurrence of any ≥ Grade 3 of amylase and/or lipase. If asymptomatic Grade 2 elevations of lipase and/or amylase occur again at the reduced dose, participants will be discontinued permanently from study treatment.
 
iAntidiarrheal medication is recommended at the first sign of abdominal cramping, loose stools or overt diarrhea.
	

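### Table 6-9 gives isolated Grade 3 bilirubin on nazartinib alone two opposite actions for resolution within 14 days, and no branch for later resolution

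*Protocol*

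**What the plan says.** Table 6-9 applies when nazartinib is continued as the only study drug. For isolated total bilirubin Grade 3 it recommends holding nazartinib, with liver tests at least weekly, until bilirubin is back to 1.5 x ULN or below. Two bullets follow:

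- First bullet: "If fully resolved in ≤14 days, then resume at ↓ 1 dose level".
- Second bullet: the same condition, resolution in ≤14 days, followed by "days, then discontinue nazartinib. The participant should be monitored weekly" and further follow-up to baseline or stabilization.

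The row has no third bullet.

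The Grade 2 bilirubin row directly above begins "If fully resolved in ≤14 days, then resume at same dose level" and pairs this with a reduced dose after more than 14 days. The Grade 4 row reads "Mandatory: Permanently discontinue nazartinib"; the Grade 3 row is only a recommendation.

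Section 6.3.1 adds a general rule: a drug-related interruption of more than 21 days, counted from the intended day of the next scheduled dose, requires discontinuation unless stated otherwise.

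**The concern.** A dose-modification row should send each outcome to one action. Read literally, this one sends a participant whose bilirubin recovers within 14 days to both a restart one level lower and a stop. It sends a participant who recovers later to neither.

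What is at stake is consistent handling of nazartinib after a liver signal. Two sites could treat the same event differently and both be following the table, and the stop for slow recovery that the row appears to intend is not written in it.

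**Working it through.** There is no figure to reproduce. The check sets the branch conditions side by side.

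**Rows of Table 6-9 that split on resolution time**

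| Row | First condition and action | Second condition and action | Complementary? |
|---|---|---|---|
| Bilirubin G2 | ≤14 d: same dose | >14 d: one level lower | yes |
| Bilirubin G3 | ≤14 d: one level lower | ≤14 d: discontinue | **no** |
| AST/ALT G3, baseline ≤3.0 x ULN | ≤14 d: same dose | >14 d: one level lower | yes |
| Amylase/lipase G3 | ≤14 d: same dose | >14 d: one level lower | yes |
| Thrombocytopenia G3 | ≤7 d: same dose | >7 d: one level lower | yes |
| Fatigue G3 | ≤7 d: same dose | >7 d: one level lower | yes |

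Three of the four 14-day rows, and five of all six, are complementary. Bilirubin Grade 3 is the only exception.

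**What the Grade 3 row leaves, by time to resolution**

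- By day 14: two incompatible actions.
- About days 15 to 21 (21 − 14 = 7 days): no branch. The hold instruction continues and nothing authorises a restart. The window is approximate because the 21-day limit counts from the next intended dose.
- Beyond 21 days: Section 6.3.1 requires discontinuation if the interruption is drug-related.

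**Could other text settle it?**

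- Footnotes b and g cover only purely indirect hyperbilirubinemia with hemolysis excluded.
- Footnote f concerns combined elevations below their own thresholds and says "please follow the instructions for isolated elevation of total bilirubin and isolated elevation of AST/ALT", which leads back to this row.
- Table 6-7 (both drugs) has no split by resolution time at Grade 3. It resumes nazartinib at the same dose once resolved, then continues "If no recurrence of grade 3 toxicity after 7 days of nazartinib monotherapy, resume capmatinib at ↓ 1 dose level". It cannot supply the missing branch.
- Table 6-8 (capmatinib alone) shows the likely model. Grade 3 bilirubin there reads "If fully resolved in ≤ 7 days, resume at ↓ 1 dose level", with permanent discontinuation if resolution takes more than 7 days.
- Section 6.3.4.2 and Table 6-17, on liver follow-up, are not in the text at hand, so their content could not be checked.

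**Who can reach the row**

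The Amendment 07 rationale states that nobody in Phase Ib or Groups 1 to 4 is still on treatment. That leaves Group 5 (about 30 planned): participants who progress on capmatinib, add nazartinib, permanently stop capmatinib and then have an isolated Grade 3 bilirubin rise. Table 6-7 has at least five routes that stop capmatinib permanently without stopping nazartinib: febrile neutropenia resolving in more than 7 days, creatinine Grade 4, amylase/lipase Grade 4, pancreatitis of Grade 3 or higher, and peripheral edema Grade 4. The protocol gives no expected number.

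**The case against.** The strongest objection is that the finding rests on one comparison sign, which falls just after a page break in text read from PDF. In the same row the footnote marker on the Grade 3 label came through as 9 where the Grade 4 label has g, and in Section 4.1 the sign before the 1% incidence of de novo T790M is garbled. A misread therefore cannot be excluded. Against it, the AST/ALT Grade 3 row after the same page break kept its two limits distinct; its slow branch, >"14 days, resume at" one level lower, came through intact. The point stands on the text as supplied, subject to a look at the source page.

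Second, the slip is visible and the intended pattern can be read from the neighbouring rows. A site that followed the wrong bullet after quick recovery would stop the drug, which is the cautious direction. That is fair and limits the consequence, but sites should not have to repair a dosing row by inference.

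Third, Section 6.3.1 allows case-by-case exceptions after discussion with the sponsor and describes continuing on one drug alone as exceptional and likewise discussed. Unsupervised misapplication is therefore less likely. This also stands.

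A reader might infer that slow recovery leaves sites free to restart between about days 15 and 21. The text does not support that: the drug is on hold, no branch releases it, and the 21-day rule then ends treatment. A reader might also see a threat to the Group 5 efficacy result. The primary endpoint is response on capmatinib monotherapy, before nazartinib is added, so it is not affected.

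**Conclusion.** As supplied, the row is wrong: one condition leads to two opposite actions, and resolution after 14 days has no branch. It is a textual inconsistency in an operative stop/restart rule rather than a design choice. For quick recovery the instruction is ambiguous. For slow recovery the intended stop is unwritten and the outcome defaults to a continued hold, then discontinuation once a drug-related interruption exceeds 21 days.

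The size is minor. The affected group is a small subset of about 30 planned participants and may be empty. Purely indirect hyperbilirubinemia with hemolysis excluded, indirect changes in Gilbert syndrome, and combined elevations that meet their own row are all outside it. The response rate, the interim futility rule and the statistical design are unaffected.

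The conclusion assumes that the second sign is ≤ on the source page and that the liver follow-up sections not at hand do not already settle the matter.

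**What to change.** Check the Grade 3 bilirubin row on the source page of Table 6-9. If both bullets show ≤14 days, change the sign in the second to >14 and leave its action, discontinuing nazartinib, as it is. The row then has the same time split as the Grade 2 row above it and the reduce-or-stop pattern of Table 6-8. No other row needs to change for this.

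The cost is one sign in one table cell and a line in a clarification letter to sites. If the source already reads >14, nothing needs to be done.

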## 6.3 Dose modifications for toxicities

### 6.3.1 Dose modification and dose interruption

For participants who do not tolerate the protocol-specified dosing schedule due to drug related toxicities, dose interruptions and/or reductions are recommended in order to allow participants to continue the study treatment. For the dose escalation part of the study, dose reductions during cycle 1 are only allowed if a DLT is observed and recorded.

Table 6-7 provides recommendations for dose modification and dose interruption (i.e., interruption and re-initiation criteria for nazartinib and capmatinib treatment).

Refer to Table 6-5 and Table 6-6 for recommended dose reduction steps for the Phase II part of the study.

If, due to study drug related toxicity, a participant requires a dose interruption of >21 days from the intended day of the next scheduled dose, then the participant must be discontinued from the study treatment unless described otherwise.

Each participant is only allowed two dose reductions on each drug. In addition, a participant must discontinue treatment with nazartinib and capmatinib if, after treatment is resumed at a lower dose, the toxicity recurs with the same or worse severity.

Exceptions on dose interruptions and modifications can be made on a case by case basis after discussion with Novartis and Investigator.

In exceptional cases, after discussion with Novartis, participants may be allowed to continue treatment or resume treatment with only one of the investigational drugs.

All dose interruptions or modifications must be recorded on the Dosage Administration Record CRF.

In case of study treatment interruption, visit schedule should still be followed and assessments performed as per Table 7-1 and Table 7-2.

After dose modification, re-escalation to a previous dose level is not permitted apart from the exceptional cases described in Table 6-14 and Table 6-15.

Events not included in the study protocol or the reference guidance documents should be managed according to local practices.

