Grade 3 (> 5.0 - 20.0 × ULN)	
Omit study treatment. Monitor LFTsc weekly, or more frequently if clinically indicated until resolved to ≤ grade 1, then resume nazartinib at the same dose level:
 
 
• If resolved in ≤ 7 days, then resume capmatinib at same dose level
 
• If resolved in > 7 days, then resume capmatinib at ↓ 1 dose level
 
• If recurrence during nazartinib monotherapy, omit study treatment until resolved to ≤ grade 1, then resume nazartinib at ↓ 1 dose level
 
• If no recurrence after 7 days of nazartinib monotherapy at ↓ 1 dose level, then resume capmatinib at ↓ 1 dose level
 

Grade 4 (> 20.0 × ULN)	Mandatory: Permanently discontinue both study drugs.

Worst toxicity CTCAE a Grade (value)	Recommendation
	Repeat LFTs c as soon as possible, preferably within 48-72 hours from awareness of the abnormal results; monitor LFTs c weekly, or more frequently if clinically indicated, until resolved to baseline or stabilization over 4 weeks.
Combinedd elevations of AST or ALT and concurrent Total bilirubinf	

For participants with normal baseline ALT and AST and total bilirubin value: AST or ALT > 3.0 × ULN combined with total bilirubin > 2.0 × ULN without evidence of cholestasise
 
or
 
For participants with elevated baseline AST or ALT or total bilirubin value: [AST or ALT > 3x baseline or [AST or ALT > 8.0 × ULN], whichever is lower, combined with [total bilirubin >2x baseline AND >2.0 × ULN]
	
Permanently discontinue nazartinib and capmatinib in the absence of signs of cholestasis, hemolysis, and if alternative causes of the liver injury have been excluded (e.g., concomitant use of hepatotoxic drug(s), alcoholic hepatitis, viral hepatitis etc.) Repeat LFTsc as soon as possible, preferably within 48 hours from awareness of the abnormal results, then with weekly monitoring of LFTsb, or more frequently if clinically indicated, until AST, ALT, or bilirubin have resolved to baseline or stabilized over 4 weeks.

METABOLICh	
Amylase and/or lipase elevation	

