Grade 1 or 2	Maintain dose level, consider to initiate appropriate support medication. For any intolerable grade 2 (e.g. limiting instrumental activities of daily living), consider omitting the dose until resolved to ≤ grade 1, then resume either at same dose or ↓ 1 dose level.
Grade 3	Omit dose until resolved to ≤ grade 1, then resume at ↓ 1 dose level
Grade 4	Permanently discontinue capmatinib

All dose modifications should be based on the worst preceding toxicity.
 
a Common Toxicity Criteria for Adverse Events (CTCAE version 5.0).
 
b “Combined” defined as: total bilirubin increase to the defined threshold concurrently with ALT/AST increase to the defined threshold
 
c “Cholestasis” defined as: ALP elevation (> 2.0 x ULN and R value (ALT/ALP in x ULN) < 2.0) in participants without bone metastasis, or elevation of ALP liver fraction in participants with bone metastasis
 
d If combined elevations of AST or ALT and total bilirubin do not meet the defined thresholds, please follow the instructions for isolated elevation of total bilirubin and isolated elevation of AST/ALT, and take a conservative action based on the degree of the elevations (e.g. discontinue treatment at the situation when omit dose is needed for one parameter and discontinue treatment is required for another parameter). After all elevations resolve to the defined thresholds that allow treatment re-initiation, re-start the treatment either at the same dose or at one dose lower if meeting a criterion for dose reduction
 
* Note: If total bilirubin > 3.0 x ULN is due to the indirect (non-conjugated) component only, and hemolysis as the etiology has been ruled out as per institutional guidelines (e.g., review of peripheral blood smear and haptoglobin determination), then ↓ 1 dose level and continue treatment at the discretion of the investigator
 
** Note: antidiarrheal medication is recommended at the first sign of abdominal cramping, loose stools or overt diarrhea
 
*** During the whole duration of treatment with capmatinib, the participant is recommended to use precautionary measures against ultraviolet exposure (e.g., use of sunscreen, protective clothing and avoid sunbathing or using a solarium intensively)
	

**Table 6-9 Dose modifications for nazartinib (if capmatinib permanently discontinued and nazartinib continued as monotherapy)**

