Grade 3: >5.0 - 10.0 x ULN AND For participants with baseline value > 3.0 -5.0 x ULN	Maintain dose level. Repeat LFTs b as soon as possible, preferably within 48-72 hours from awareness of the abnormal results; if abnormal lab values are confirmed upon the repeat test, then monitor LFTs b , weekly, or more frequently if clinically indicated, until resolved to $\leq 5.0$ x ULN
Grade 3: >5.0 - 10.0 x ULN AND If AST or ALT > 5 x ULN in participants with baseline AST or ALT $\leq 3$ x ULN, or if AST or ALT > 8 x ULN in participants with baseline AST or ALT > 3 x ULN but $\leq 5$ x ULN	Mandatory: Immediate testing for viral hepatitis infection or reactivation should be performed, see Section 6.3.2 . Participants who have HBV-DNA or HCV-RNA monitoring during the study should be re-tested immediately
Grade 3: >5.0 - 10.0 x ULN AND > 10.0 - 20.0 x ULN	Mandatory: Omit dose. Repeat LFTs b as soon as possible, preferably within 48-72 hours from awareness of the abnormal results; monitor LFTs b weekly, or more frequently if clinically indicated, until resolved to $\leq$ Grade 1 (or to baseline), then resume at $\downarrow$ 1 dose level.
Grade 4: > 20.0 x ULN	
For participants deriving clinical benefit upon investigator's judgement	Mandatory: Omit dose. Repeat LFTs b as soon as possible, preferably within 48-72 hours from awareness of the abnormal results; monitor LFTs b weekly, or more frequently if clinically indicated, until resolved to $\leq 3$ x ULN (or $\leq 5$ x ULN for participants with baseline value > 3.0 -5.0 x ULN),

Worst toxicity CTCAE a Grade (value) during a cycle of therapy	Recommendations
	then resume at ↓ 1 dose level. Only 1 dose reduction is allowed; if reoccurs at > 5 x ULN, discontinue nazartinib
For all other participants:	Mandatory: Permanently discontinue participant from study drug treatment Repeat LFTs b as soon as possible, preferably within 48-72 hours from awareness of the abnormal results; monitor LFTs b weekly, or more frequently if clinically indicated, until resolved to baseline or stabilization over 4 weeks.
Combinedd elevation of AST or ALT and concurrent Total bilirubinf	

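### Table 6-9: the Grade 3 AST/ALT row that orders mandatory omission of nazartinib has a condition no value can meet, leaving >10–20 x ULN without an isolated AST/ALT dosing row as printed

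*Protocol*

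**What the plan says.** Section 6.3.1 of the Protocol holds three dose-modification tables. Table 6-7 covers the combination, Table 6-8 covers capmatinib alone, and Table 6-9 is titled "Dose modifications for nazartinib (if capmatinib permanently discontinued and nazartinib continued as monotherapy").

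In the isolated AST/ALT block of Table 6-9, four rows begin with the same Grade 3 band of >5.0–10.0 x ULN followed by AND:

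- **Baseline up to 3 x ULN:** omission is recommended. Dosing resumes at the same level if the elevation resolves within 14 days, otherwise one level lower.
- **Baseline >3–5 x ULN**, labelled "Grade 3: >5.0 - 10.0 x ULN AND For participants with baseline value > 3.0 -5.0 x ULN": the dose is maintained, with repeat liver tests.
- **Viral hepatitis testing**, whose label begins "Grade 3: >5.0 - 10.0 x ULN AND If AST or ALT > 5 x ULN in participants with baseline" and continues with baseline-specific triggers (>5 x ULN for baseline up to 3, >8 x ULN for baseline >3–5): immediate testing is mandatory.
- **Mandatory omission**, labelled "Grade 3: >5.0 - 10.0 x ULN AND > 10.0 - 20.0 x ULN": omit, repeat liver tests, and resume one level lower.

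The next entry is "Grade 4: > 20.0 x ULN". The sister tables use a single Grade 3 band: "Grade 3 (> 5.0 - 20.0" x ULN in Table 6-7 and "Grade 3 (> 5.0 - 20.0 x ULN" in Table 6-8.

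**The concern.** A value cannot lie both in >5–10 and in >10–20 x ULN, so the mandatory-omission row can never be triggered as printed. It is also the only row that mentions >10–20 x ULN, the upper part of Grade 3. A literal reader with a participant in that band finds no isolated AST/ALT row that applies. What is at stake is the clarity of an operative hepatic safety rule, and in particular the mandatory status of the action. Dose intensity and dose interruption are tolerability endpoints in Group 5, but nothing suggests that this wording would change them measurably.

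**Working it through.** **Inputs.** The row labels come from Table 6-9. The Grade 3 range comes from Tables 6-7 and 6-8 (>5 to 20 x ULN). Both baseline strata can occur in Group 5: exclusion criterion 17 in Section 5.3 allows AST/ALT up to 5 x ULN at entry with liver metastases.

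**Step 1: the condition.** Write the bands as (5, 10] and (10, 20]. Their intersection is empty, so no value meets the label.

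**Step 2: which dosing row applies.** The hepatitis row is left out here because it sets testing and not dose.

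| AST or ALT (x ULN) | As printed | AND read as 'or' | Relabelled >10–20 |
|---|---|---|---|
| 8 or 10, baseline up to 3 | recommended omission | recommended omission and mandatory omission | recommended omission |
| 8 or 10, baseline >3–5 | maintain | maintain and mandatory omission | maintain |
| 10.5, 15 or 20, either baseline | no row | mandatory omission | mandatory omission |
| 21, either baseline | Grade 4 | Grade 4 | Grade 4 |

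As printed, the gap is exactly >10–20 x ULN in both strata. The 'or' reading closes the gap but sets two rows against each other at >5–10 x ULN. For baseline >3–5 they order opposite actions. In the neighbouring rows AND plainly means that the band and the baseline condition must both hold. With the relabelled row, every value above ULN falls in exactly one dosing row.

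**Step 3: what applies in the gap.** The catch-all row for other adverse events in Table 6-9 recommends, at Grade 3, omission until Grade 1 or lower and then one dose level lower. That is nearly the same dose action, but it is a recommendation where the unreachable row is mandatory, and its heading suggests events without a block of their own. Section 6.3.1 also sends events not covered by the Protocol or its reference guidance to local practice. The combined AST/ALT and bilirubin row does not fill the gap, because it also requires raised bilirubin.

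**Step 4: the hepatitis testing row.** Its own triggers have no upper limit within Grade 3, but the prefix adds one at 10 x ULN.

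| Baseline | As printed | Prefix removed, Grade 3 label kept |
|---|---|---|
| up to 3 x ULN | >5 to 10 x ULN | >5 to 20 x ULN |
| >3–5 x ULN | >8 to 10 x ULN | >8 to 20 x ULN |

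So as printed, mandatory testing under this row stops applying just as the elevation becomes worse.

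**The case against.** **The table may simply have been broken in the PDF reading.** Four consecutive labels share one prefix, which could be a spanning cell copied down. This cannot be excluded from the text at hand. It is the less likely explanation. In the same block the Grade 4 label is not copied into its two sub-rows, and continued cells in Table 6-4 are left blank. The Table 6-4 comparison is weaker, because there the label has its own column. A copied cell would also not obviously supply the word AND. What stands is that the printed page should be checked first.

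**Nobody would misread it.** An investigator seeing 15 x ULN would find the only row naming that band and follow it. This is largely right, and it is why the point is low severity. It does not make the printed condition correct.

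**Reach is tiny.** No participant from Phase Ib or Groups 1 to 4 remains on treatment (Amendment 07 rationale). Table 6-9 can therefore matter only for Group 5 participants (about 30 planned) who progress on capmatinib, enter the combination extension, stop capmatinib permanently and continue nazartinib alone. Section 6.3.1 describes single-drug continuation as exceptional. This stands in full.

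**Stronger readings a reader might infer.** One is that participants at >10–20 x ULN would be left without any instruction, or forced off treatment. The catch-all row and the local-practice clause answer the first. Section 6.3.1 answers the second: "Exceptions on dose interruptions and modifications can be made on a case by case basis after discussion with Novartis and Investigator". Another is that liver-test follow-up or hepatitis testing would be lost. The documents do not support that either. The text of Sections 6.3.2 and 6.3.4 and Tables 6-16 and 6-17 is not shown, and these may cover both.

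**Conclusion.** The point holds as a low-severity wording error in a safety table. The condition for mandatory omission is empty, the band >10–20 x ULN has no isolated AST/ALT dosing row as printed, and reading the conjunction as 'or' creates a contradiction at >5–10 x ULN for baseline >3–5. The intended band is clear from the neighbouring rows and from the Grade 3 range in Tables 6-7 and 6-8, so this is a mislabelled row and not a missing policy. The size is a matter of rule coverage only: the Protocol gives no frequency for such values. No effect on any endpoint, analysis or sample size follows. The conclusion assumes that the label is printed as read. Nothing is concluded about Section 6.3.2, or about hepatitis testing above 20 x ULN, which the Grade 3 label leaves outside this row in any case.

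**What to change.** After checking the printed page, make two label changes in Table 6-9:

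1. Relabel the mandatory-omission row as Grade 3: > 10.0 - 20.0 x ULN, with the action unchanged.
2. Remove the >5.0–10.0 x ULN band and the AND from the viral hepatitis testing row, keeping its Grade 3 label, so that its own triggers (>5 or >8 x ULN by baseline) apply across Grade 3. Read the result against Section 6.3.2 when making the edit.

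The cost is two row labels at the next amendment. Dose actions, data collection, sample size and analysis do not change.
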